Imputation for missing data (multiple imputation using chained equations, [7]) will be performed for missing primary and secondary outcomes data. Variables used for imputation will include treatment allocation, randomization sequence, and period; all other primary and secondary outcomes variables, plus selected auxiliary variables designed to facilitate imputation of outcomes variables including baseline AHI, BMI, on-treatment side effects (where available), self-reported questionnaire outcome scores (where available), and any additional measures that are discovered to meaningfully improve model quality. For each imputed dataset, the routine will impute missing data using 50 iterations. Stochastic noise will be added to each imputed missing data result to match population heterogeneity. After each imputed dataset is generated, the primary model analysis will be repeated and recorded (similar approach for secondary analyses). In total, 20 imputed datasets will be generated; pooled model coefficients and 95%CI (Rubin's rules) will be used to generate a single imputed beta coefficient for the effect of treatment allocation on each outcome variable.

Interim analyses will not be performed (removed from plan per discussions with DSMB at study initiation).

PARTNERS HUMAN RESEARCH COMMITTEE DETAILED PROTOCOL

Version: April 11th, 2024

Power analysis. Sample size is based on the secondary outcome with the smallest expected effect size: 48 patients will provide 80% power to detect a clinically-significant reduction in the Epworth Sleepiness Scale of 2 points (expected SD≈4.8) [20, 54, 55] (alpha=0.05). With 48 patients, the power to detect a clinically-significant change in the primary outcome variable (50% reduction in apnea-hypopnea index, expected SD≈19% from preliminary study) exceeds 99.9% (alpha=0.05). *Other secondary outcomes:* Power to detect A) an increase in nadir oxygen saturation by 5 percentage points (expected SD≈8%, preliminary data) is 98.9%; B) a reduction in arousal index of just 10% (expected SD≈21%, preliminary data) is 89.8%; C) an increase in the Functional Outcomes of Sleep Questionnaire score of +2 (expected SD≈3.1[55]) is 99.2%. The study will also be adequately powered to assess effects on the AHI separately in men (N=32; power>99%) and women (N=16; power>99%). By studying 48 patients (rather than a lower number), we expect results to be generalizable across groups by age, sex, race/ethnicity, obesity; we will also have the capacity to determine the physiological mechanisms determining responses to therapy, a major goal of this work (see Aim 2). Recruitment will continue until 48 patients have completed both arms (active and placebo) of the study; based on a ~20% dropout rate we expect to randomize 60 patients.

Aim 2

Statistical analysis plan—Physiological determinants. Tests are designed to illustrate that each trait *explains* individual differences in the *response to therapy* (defined below). We will prospectively-test the hypothesis that greater pharyngeal collapsibility determines a reduced response to therapy (linear regression, *response to therapy* versus Vpassive). We will also separately test the hypotheses that a reduced muscle responsiveness, reduced baseline muscle activation, a higher arousal threshold, and a lower loop gain will facilitate a greater response to therapy (linear regression). The primary outcome variable (*response to therapy*) will be calculated by assessing the percent reduction in AHI from baseline with intervention (at 1 month) minus the percent reduction in AHI from baseline with placebo, i.e. consistent with Aim 1. Per-protocol analysis will be used because the study aims to explain inter-individual physiological responses. All questions are of separate scientific relevance and will not be adjusted for multiple comparisons. Multivariable regression will confirm whether baseline physiological variables remain predictive after adjusting for baseline apnea-hypopnea index.

Commonly, knowledge of multiple traits *in combination* best predicts outcomes. We will therefore perform a multivariable linear regression analysis (with interactions and squared terms, as needed, to capture non-linear relationships when evident) to describe how the traits combine to determine responses to therapy. This approach has been used successfully previously [46] and has strong physiological rationale (i.e. in those with milder collapsibility, higher loop gain leads to therapeutic failure).

Statistical analysis plan—Clinical predictors. We will build a multivariable model to *predict* individual differences in the response to therapy (defined above) using 1) routine baseline polysomnographic variables (including ratio of apneas to total events), and 2) estimated polysomnographic phenotypic traits (described above). In both cases, as performed previously

PARTNERS HUMAN RESEARCH COMMITTEE DETAILED PROTOCOL

Version: April 11th, 2024

[56], we will use multivariable linear regression (original terms, interactions, squared terms i.e. quadratic model). Non-contributory terms will be removed incrementally to provide a final regression model (backwards elimination with $P>0.157$, equivalent of AIC criteria [57-60]); this simple approach previously outperformed other approaches on out-of-sample data including use of looser criteria (e.g. $P<0.05$), stricter criteria (e.g. $P<0.5$), regularization methods e.g. LASSO, and nested cross-validation [46]. The predictive value of the model will be assessed using leave-one-out cross-validation to handle overfitting, with the entire backwards elimination process repeated for each loop in the cross-validation process. If results are promising, a separate test set will be studied in future for validation.

Power analysis. *Physiological determinants:* 36 patients will provide 88% power (alpha=0.05) to detect a physiologically-significant association ($R^2=0.25$) between each gold-standard phenotypic trait and the response to therapy (defined above). In previous studies, 14-20 patients were sufficient to show significant multivariable associations between the response to therapy and two variables (e.g. loop gain and collapsibility) [61] supporting the view that 36 patients will be sufficient for four gold-standard traits. 36 patients were also sufficient for multiple regression in a recent study [46] using multiple traits to predict outcomes. *Clinical predictors:* 48 patients will provide 81% power to detect modest independent associations ($R^2=0.2$) between each predictor and the response to therapy. We expect 36/48 patients taking part in Aim 1 to complete the Aim 2 study.

VII. RISKS AND DISCOMFORTS

The study incorporates a trial of two established agents separately approved for other conditions, that have not yet been assessed in combination for OSA treatment for as long as 1 month. We consider the study to be more-than-minimal risk. Nonetheless, we feel the risks are reasonable given the potential benefits of providing a future treatment for OSA. Anticipated risks and discomforts are listed below:

Clinical Sleep Study: The equipment used for assessing sleep (paste on electrodes) is standard and poses no risk. The electrodes may be mildly uncomfortable and could cause some sleep interruption. Thus subjects may feel somewhat tired the day following this study.

Atomoxetine: Common side effects include dry mouth, fatigue, irritability, nausea, decreased appetite, constipation, dizziness, sweating, insomnia, dysuria, dysmenorrhea, sexual problems, decreased libido, urinary retention or hesitancy, increased obsessive behavior, weight changes, palpitations, increases in heart rate and blood pressure.

Uncommon side effects (<1%) include tachycardia, rhythm disturbance, suicidal ideation, aggressive behavior, mood swings, serious allergic reaction. Rare side effects (<0.1%) include seizures, alopecia, hallucinations, liver injury.

Oxybutynin: Common side effects include: urinary retention, dry mouth, dry eyes, dry skin, constipation, nausea, facial flushing, dizziness, headache, somnolence/fatigue, confusion, dyspepsia, diarrhea, blurred vision, vomiting. Uncommon side effects (<1%) include drowsiness, light sensitivity, abdominal discomfort/pain, anorexia, decreased appetite,

PARTNERS HUMAN RESEARCH COMMITTEE DETAILED PROTOCOL

Version: April 11th, 2024

dysphagia. Rare side effects (<0.1%) include restlessness, disorientation, concentration difficulties, phototoxicity, erectile dysfunction.

Physiological Sleep Study:

- Esophageal catheters: Ventilatory drive/effort will be monitored using an intraesophageal diaphragm EMG catheter. There is some discomfort passing the catheters through the nose and gagging can occur. The risk of aspiration must be considered in a subject where a mask is in place and a catheter has been inserted. Although this is a potential risk, we believe the likelihood to be quite small for several reasons. Once in place, the catheter causes little gagging. All subjects will have fasted for three hours prior to the procedure and thus their stomach content is minimal. Finally, the mask can be easily removed. For these reasons we believe aspiration to be a minimal risk.
- Lidocaine 4%: If the subjects have any history of lidocaine allergy, they will be excluded from Aim 2 of the study. Excessive use of lidocaine can cause seizures, but this is reported with much higher doses than will be utilized in this study. Note, lidocaine does taste unpleasant and the subjects will be informed of this.
- CPAP changes during sleep: The only real risk with the procedures for CPAP changes is sleep disruption. The ventilation device is not uncomfortable and actually facilitates ventilation. However, the procedures may awaken the subject leading to poor quality sleep.

Stopping criteria:

For stopping a treatment period: Any adverse event that in the judgment of the investigator necessitates the subject stopping to protect their safety. Additional criteria include: abuse, diversion or misuse of the agents; clinically significant hallucinations, amnesia, delusional thinking, delirium, manic symptoms, aggressive behavior, suicidality, homicidal behavior, agitation, confusion, or convulsions/seizures.

For stopping catheter placement: Vomiting, or more-than-mild gagging causing discomfort that in the judgement of the investigator necessitates stopping catheter placement. Data collection will continue in order to obtain other variables.

For stopping the overnight physiological study: Difficulty sleeping with study equipment in place such that by 3 am, or another time in the judgement of the investigator, the subject remains awake.

Thus, we believe that all possible safeguards are in place to minimize the risk.

VIII. POTENTIAL BENEFITS

Benefits to medical community. This study provides a unique opportunity to gain insight into a combination pharmacological therapy for OSA, including factors involved in its successful

PARTNERS HUMAN RESEARCH COMMITTEE DETAILED PROTOCOL

Version: April 11th, 2024

resolution. The results may, in the future, improve our understanding of sleep apnea and lead to improved strategies for therapies.

Benefits to individual subjects. Although it is unlikely that there will be any direct physical benefit to the subjects from participating in this study, we will make known to each subject, if requested, some of the information we have gathered from their baseline PSG. However, if previously unknown abnormalities of sleep and breathing are encountered, this information will be passed onto the subject. In order to maintain the subjects' privacy, results can be forwarded to the primary care physician or clinician only at the request of the subject.

IX. MONITORING AND QUALITY ASSURANCE

Data and Safety Monitoring

The Principal Investigator ([name]) will be responsible for maintaining Quality Assurance, and will delegate tasks to study staff including [name] (i.e. IRB regulatory binder maintenance, source documentation completeness) and [name] (i.e. database entry and monitoring). A licensed physician investigator study staff member ([name]) will be designated as the lead study clinician and responsible provider for subjects participating in the study.

The current study comprises a single-center randomized-controlled clinical trial. Based on conversations with the NIH, in an abundance of caution, a formal Data and Safety Monitoring Board (DSMB) will be implemented. See the Data and Safety Monitoring Plan for details. The DSMB will independently monitor safety and quality assurance. The board will review all adverse events in order to classify them as serious adverse events, minor adverse events, and whether they are anticipated or unanticipated, and study related or unrelated as per our IRB rules and the NHLBI policy. The DSMB will strictly adhere to the definitions below (see **Definitions**). Adverse events and severe adverse events will be reported to the PHRC and NIH according to respective guidelines.

Ongoing results, problems, and limitations of the study will also be presented on a regular basis to the investigators in the Division of Sleep Medicine.

Adequacy of Protection Against Risks

Training

All of our laboratory personnel involved in the research of human subjects have completed the required institutional program for education in the protection of human research subjects and their confidentiality. The institutional educational program consists of the review of regulatory and informational documents pertaining to human-subject research, passing a test demonstrating knowledge of the ethical principles and regulations governing human-subject research and signing a statement of commitment to the protection of human subjects.

PARTNERS HUMAN RESEARCH COMMITTEE DETAILED PROTOCOL

Version: April 11th, 2024

Informed Consent

Circumstances. Subjects will be recruited from two sources: 1.) The Sleep Clinic at Brigham and Women's Hospital. Patients admitted to our clinic fill out a questionnaire. One of the questions asks if they would like to be contacted regarding research studies. If they answer "yes", then one of our study staff will contact them by phone regarding our particular study. 2.) The community: We frequently recruit subjects with obstructive sleep apnea by advertising in various newspapers, and thus we will use this as a source. Interested persons will be screened over the phone by a study staff member and given details about the study with a chance to ask questions.

Obtaining consent. Subjects will then be mailed, faxed or secure-emailed a copy of the consent form to read at their convenience (at least 24 hours before signing the consent; typically 1-4 weeks ahead of time). They will be explicitly informed that participation in the research study is completely voluntary, that their medical care will not be adversely affected should they choose not to participate, and that they may stop the study at any time. The PI and/or senior co-investigator will interview each potential subject. Consent will be obtained by a licensed physician study investigator in-person prior to the first overnight study. At that time, the protocol will be explained in full detail, including the risks and benefits, and the subject will have a chance to ask more questions and discuss the study with a physician. Signature of the consent form by the subject and the investigator will be used for documentation.

Protection Against Risks

We will attempt to minimize the risk to subjects as follows:

- i. All subjects will be relatively healthy and without medically important disorders except for obstructive sleep apnea. History and physical will be assessed by a physician to confirm health and absence of exclusion criteria prior to administration of medications. A physician will also check on subjects while they are admitted to the Clinical Center of Investigation for overnight studies and will have ongoing overnight nursing coverage. A physician will be on-call throughout the stays. Should subjects need medical assistance, the nurse will notify the study physician and the PI.
- ii. Identifiable data will be kept confidential by de-identifying (coding) subjects. All subject data are stripped of identifiable information, coded with a four-digit number, and kept online using a secure network service with a daily backup in accordance with Institutional policy. Paper forms with identifiable information (consent forms) will be stored in a locked file cabinet accessible only by study staff. Links between subject codes and identifiers are kept exclusively in a secure password-protected database. Only the study staff will have access to the subject identifying information.
- iii. All studies will be conducted by an experienced investigator knowledgeable in all aspects of the procedures utilized. Breathing variables, including arterial oxygen saturation, and heart

**PARTNERS HUMAN RESEARCH COMMITTEE
DETAILED PROTOCOL**

Version: April 11th, 2024

rate will be monitored continuously in all studies. Blood pressure monitoring will be performed on arrival, before sleep, and after sleep at all study visits.

- iv. Resuscitation equipment is readily available should the need arise. CPAP and 100% oxygen are available in the study rooms and can be quickly provided to the patient if needed. However, this seems unlikely.
- v. While the clinical sleep studies in the laboratory are noninvasive, the physiological studies (with esophageal catheterization) are somewhat invasive and there is a risk that subjects may be sleepier than usual in the morning. Thus, subjects will have the opportunity to sleep without instrumentation for as long as they would like before driving home. We will also offer a cab voucher to those who did not drive.
- vi. Women will have a urinary human chorionic gonadotropin test at each study visit to confirm absence of pregnancy.
- vii. In the case of adverse effects, each subject will be given the responsible study clinician's ([name]) cell phone number, and the principal investigator's cell phone number to contact at any time (24/7) regarding questions or complications; subjects will be strongly encouraged to call the study team. [name] will facilitate referrals for further medical care when appropriate.
- viii. During each period of the study, subjects will be contacted (e.g. telephone) for systematic safety assessment (adverse event checklist) according to a regular schedule (see above), including during the washout period after study completion. Subjects will additionally be asked to contact study staff if adverse events occur.
- ix. When used clinically, the study medications are not tapered-down before discontinuation (stopping). We also emphasize that there is data demonstrating no significant rebound/withdrawal effects of atomoxetine (in contrast to other noradrenergic agents/antidepressants) [62]. Nonetheless, subjects will be asked to contact the lead study clinician to discuss any concerning rebound/withdrawal effects after stopping study medications, and will receive advice on appropriate actions to mitigate symptoms, including delaying further study periods or discontinuation (see criteria below) when appropriate.
- x. Unanticipated problems involving risks to subjects or others including adverse events will be reported to the Human Research Committee as soon as possible and within 5 working days/7 calendar days for review according to the HRC adverse event reporting guidelines.
- xi. Incidental findings are rare. Nonetheless, any findings will be communicated with the subjects by MD study staff. It is possible that subjects may discover a pregnancy. It is possible that study staff may witness a cardiac arrhythmia (e.g. atrial fibrillation). The lead study clinician will facilitate referrals for further medical care as appropriate.
- xii. Our study seeks to recruit some individuals who 1) have “clinically-suspected” OSA, and 2) would refuse an offer of CPAP even if clinically recommended. In subjects who are discovered to have OSA on baseline polysomnography: The lead study clinician will 1) discuss the study findings with the participant, 2) explain that CPAP is the standard of care for OSA, 3) emphasize that our priority is for patients to be optimally treated over

PARTNERS HUMAN RESEARCH COMMITTEE DETAILED PROTOCOL

Version: April 11th, 2024

participation in the study, 4) provide information on drowsy driving/risks of hypersomnolence, and 5) facilitate clinical referral (BWHF Sleep Disorders clinic) as appropriate for interested participants. Further participation in the study can be delayed, or declined, per informed participant choice, to minimize the likelihood that study participation might delay appropriate clinical care.

xiii. Questionnaires can contain sensitive personal information. For example, the Functional Outcomes of Sleep Questionnaire addresses information about sexual relationships and intimacy. Subjects will complete these in a private room and can choose not to answer any questions they feel uncomfortable answering.

To minimize discomfort due to esophageal catheterization, topical anesthesia (lidocaine) is used to minimize discomfort upon placement. Subjects will also fast for 3 hours prior to catheter placement to minimize the likelihood of vomiting. No patient has vomited from esophageal catheter placement under the PI's supervision despite hundreds of placements to date.

Network Security for protecting the confidentiality of subject data

All electronic data will be stored on Partners-approved secure network platforms (i.e. Secure File Area, Dropbox Enterprise) under password protection with no access allowed to individuals outside of our research team. All paper data will be stored under lock and key with access only given to the study staff.

Definitions

Definitions are per January 2007 OHRP *Guidance on Reviewing and Reporting Unanticipated Problems Involving Risks to Subjects or Others and Adverse Events, OHRP Guidance, <http://www.hhs.gov/ohrp/policy/AdvEvntGuid.htm>*

Adverse Event (AE): any untoward or unfavorable medical occurrence in a human subject, including any abnormal sign (for example, abnormal physical exam or laboratory finding), symptom, or disease, temporally associated with the subject's participation in the research, whether or not considered related to the subject's participation in the research.

Serious adverse event (SAE): any adverse event that:

- Results in death
- Is life threatening, or places the subject at immediate risk of death from the event as it occurred
- Requires or prolongs hospitalization
- Causes persistent or significant disability or incapacity
- Results in congenital anomalies or birth defects
- Is another condition which investigators judge to represent significant hazards

Unanticipated Problem (UP): any incident, experience, or outcome that meets all of the following criteria:

**PARTNERS HUMAN RESEARCH COMMITTEE
DETAILED PROTOCOL**

Version: April 11th, 2024

- unexpected, in terms of nature, severity, or frequency, given the research procedures that are described in the protocol-related documents, such as the IRB-approved research protocol and informed consent document; and the characteristics of the subject population being studied;
- related or possibly related to participation in the research, in this guidance document, possibly related means there is a reasonable possibility that the incident, experience, or outcome may have been caused by the procedures involved in the research;
- suggests that the research places subjects or others at a greater risk of harm (including physical, psychological, economic, or social harm) than was previously known or recognized.

Adverse Events (FDA) versus Unanticipated Problems (OHRP)

- All adverse events are not necessarily unanticipated problems
- All unanticipated problems are not necessarily adverse events

Some events may be both

**PARTNERS HUMAN RESEARCH COMMITTEE
DETAILED PROTOCOL**

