- Visual Analog Scales (VAASQ) and Treatment Satisfaction (VASTS, treatment only)
- Enthusiasm for continued therapy (ECT, treatment only; i.e. subjects will answer whether they would choose to continue using the treatment if given the opportunity)

Adherence. Nightly adherence will be monitored using electronic pill containers (MEMS cap) with real-time wireless monitoring capabilities that will keep the study staff informed of adherence throughout the study; direct feedback from technology (text message), and indirect feedback from study staff will serve to maximize adherence. We will also assess adherence through patient self-report and pill counts.

Sleep study. After 1 month of treatment at home, the subject will attend an overnight sleep study at the hospital (BWH, Tower 9A) and will perform a sleep study after taking the last dose of study medication for the treatment period (see **Measurements and Equipment—Clinical**). On these treatment studies, once all the equipment has been secured, subjects will be given their medication to take (30 min before lights out).

Safety Monitoring. See Data and Safety Monitoring Plan for details. In brief:

- Incident adverse events (AE) and any serious adverse events will be monitored throughout the study period and for 2 weeks after the last dose. Patients will be contacted by telephone (days 1, 3, 7, 14, 21, 28 of intervention; 7, 14 days after completion) and in person at the 1-month visit (day 30), following a standardized framework, to ensure timely reporting and clinical assistance if required. Patients will be asked to describe the incidence and severity of common side effects by checklist and any other adverse events.
- At each study visit we will also measure
 - effects on sleep parameters (including total sleep time, proportion of REM sleep, proportion of slow wave sleep, proportion of stage 1 sleep, arousal frequency)
 - effects on sleepiness and quality of life (ESS, SAQLI, VASSQ, and FOSQ)
 - overnight heart rate and evening/morning supine blood pressure (triplicate),
 - Brief Psychiatric Rating Scale (BPRS) to monitor for the potential emergence of suicidal ideation or behavior
 - medication tolerance based on adherence

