Subjects will be mailed a Nox Medical A1 home sleep test device along with the study medication. We will ask subjects to return unused medication after each treatment arm to be disposed of by the pharmacy. They will be given detailed instructions on how to self-apply standard polysomnography (PSG) recording sensors. Sleep stage and arousals will be measured with electrodes placed on to the face. Respiratory effort belts will be placed around the chest and abdomen to measure breathing movements and body position. Oxygen saturation will be measured continuously with a pulse oximetry probe placed on the fingertip. Snoring will be detected with a small microphone positioned over the suprasternal notch and plugged into a smart phone. Breathing will be measured using a nasal cannula. Each of these devices is standard for diagnostic PSG and should not be uncomfortable.

Prior to bed, subjects will video call study staff to confirm equipment has been correctly applied and take the study medication.

The morning after the sleep study, subjects will again attend a Zoom video call with study staff. On the Zoom video call, supine blood pressure will be measured, as above, by the subject using a blood pressure monitor (sent with devices with instructions). Equipment will be removed, side effects will be assessed systematically from a list of the possible side effects of all drugs used in the trial. Subjects will complete questionnaires (see above). Subjects will then mail back the devices and questionnaires so data can be downloaded and equipment can be properly cleaned and disinfected.

Data analysis

Apneas, hypopneas, sleep stages and arousals from sleep will be scored using current AASM guidelines (hypopneas defined by at least a 30% reduction in airflow in conjunction with either 3% desaturation or arousal) by a technician blinded to the study condition.

**PARTNERS HUMAN RESEARCH COMMITTEE
DETAILED PROTOCOL**

Version: April 11th, 2024

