Subjects will receive \$100/night for participation in the three overnight clinical studies (3 overnights = \$300). Subjects will receive \$200 for participation in the overnight physiology study. An additional \$200 will be provided for successful completion of each study period (2 completed periods = \$400). Thus, in total, a subject could receive up to \$900 at study completion. If a baseline study is not needed, subject will not receive the \$100 for the study not performed. If subjects repeat a part of the entire protocol because of insufficient data collection, they will be reimbursed \$100 for any extra night. Reimbursement for parking expenses or taxi fares will be provided.

For any inpatient visits requiring a COVID-19 test prior to admission, subjects will receive an additional \$50 for each test.

Home Sleep Tests Bonus: For home sleep tests, subjects will receive a \$25 bonus for each home sleep test that is mailed back to study staff the day after the study. Therefore, they could

PARTNERS HUMAN RESEARCH COMMITTEE DETAILED PROTOCOL

Version: April 11th, 2024

receive up to \$100 for a timely return of the devices. If the subject does not send back equipment immediately, they will not receive this bonus.

VI. BIOSTATISTICAL ANALYSIS

Aim 1

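### The BPRS is the only suicidality instrument named and is first given on treatment on the last-dose night; no structured suicidality question is described for the calls made during exposure

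*Combined protocol and SAP*

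**What the plan says.** All references are to the combined protocol and SAP.

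- **Instrument and timing.** Section V, AtoOxy Treatment, Safety Monitoring has a list that opens "At each study visit we will also measure" and includes the "Brief Psychiatric Rating Scale (BPRS) to monitor for the potential emergence of suicidal ideation or behavior". No other suicidality instrument is named, and no telephone use of the BPRS is described.
- **Visits.** Section V, Reimbursement refers to "participation in the three overnight clinical studies": one at baseline and one per treatment period. There is also a physiology night, which comes before treatment. At the treatment visit the patient "will perform a sleep study after taking the last dose of study medication for the treatment period".
- **Calls.** Telephone contact is set for days 1, 3, 7, 14, 21 and 28 of each period, and for 7 and 14 days after completion. "Patients will be asked to describe the incidence and severity of common side effects by checklist and any other adverse events".
- **Frequency classes.** Section VII, Atomoxetine: "Uncommon side effects (<1%) include tachycardia, rhythm disturbance, suicidal ideation, aggressive behavior, mood swings, serious allergic reaction". Hallucinations and seizures are classed as rare (<0.1%).
- **Action on a positive item.** Section V requires immediate physician assessment of any BPRS suicidality response of very mild or higher. Participation ends if emergent suicidality is judged related to the study.
- **Stopping a treatment period.** Section VII, Stopping criteria covers any adverse event that the investigator judges to require it, and adds "clinically significant hallucinations, amnesia, delusional thinking, delirium, manic symptoms, aggressive behavior, suicidality, homicidal behavior, agitation, confusion, or convulsions/seizures".

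**The concern.** The stopping criteria are meant to act while a patient is taking drug. The instrument chosen to detect emergent suicidality reports only when dosing for that period is finished or one dose from finished. The contacts that do fall within exposure are described in terms that leave suicidal ideation outside the itemised questions, given the document's own frequency classes. Between visits, detection then depends on the patient raising the matter unprompted.

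At stake is the timeliness of detection for the gravest psychiatric risk that the document names, and how completely such events are ascertained during exposure.

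**Working it through.** The plan states no figure for this point, so there is none to reproduce. The check is day arithmetic on the schedule.

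**Step 1. Doses before the first on-treatment BPRS.** Section V gives 30 days ± 7, that is 23 to 37 days, with the visit on the last-dose night. If the BPRS is done before that night's dose, the share of doses already taken is (d − 1)/d:

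| Length of period, d | Doses before the BPRS | Share |
|---|---|---|
| 23 | 22 of 23 | 96% |
| 30 | 29 of 30 | 97% |
| 37 | 36 of 37 | 97% |

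The document does not say when in the visit the BPRS is given. If it is given the next morning, all doses precede it.

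**Step 2. What the calls ask.** Setting the call content beside the Section VII classes:

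- Suicidal ideation and aggressive behavior are stopping events classed as uncommon.
- Hallucinations and seizures are stopping events classed as rare.
- Confusion is a stopping event on the common list (oxybutynin).

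The fuller list of all possible side effects is described for the treatment visits and the morning after, not for the calls.

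**Step 3. Mean time to the next structured question.** Assume onset is uniform over a period of T days. With assessment intervals L, the mean delay is ΣL² / (2T).

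- As scheduled, T = 30, one interval: 30² / 60 = 900 / 60 = 15.0 days.
- Item asked at the existing calls and the day-30 visit, with intervals 1, 2, 4, 7, 7, 7, 2: (1 + 4 + 16 + 49 + 49 + 49 + 4) / 60 = 172 / 60 = 2.87 days.

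At the ends of the visit window:

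- T = 23: 23² / 46 = 11.5 days, against (1 + 4 + 16 + 49 + 49 + 4) / 46 = 123 / 46 = 2.7 days.
- T = 37: 37² / 74 = 18.5 days, against (1 + 4 + 16 + 49 + 49 + 49 + 81) / 74 = 249 / 74 = 3.4 days.

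These are delays to a structured question, not to any contact. The calls themselves are at most 7 days apart, with up to 9 days from the day-28 call to a day-37 visit.

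**Step 4. Scale.** Only the active period carries drug exposure, so each patient contributes one such period. The document gives only <1% for suicidal ideation with atomoxetine. As an assumption, take 0.1% to 1% per patient in this trial. The chance of at least one case is 1 − (1 − p)ⁿ:

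- 60 patients exposed (the expected number randomized): 5.8% to 45.3%.
- 48 patients exposed (the completers): 4.7% to 38.3%.

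The exclusions in Section III (recent suicide attempt or ideation, bipolar disorder, mania, psychosis) may put the true figure lower in that range or below it.

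**The case against.** The strongest reply is that the stopping rule does not depend on the BPRS. Section VII lets the investigator stop a period for any adverse event and lists suicidality without naming an instrument. Six calls ask about any other adverse events. Section IX, Protection Against Risks, items vii and viii, gives patients 24/7 telephone access to the study clinician and principal investigator and asks them to report events between calls. All of this stands. A reader might infer that suicidality cannot stop treatment during the 30 days, or that the safety rule cannot work; the documents do not support either reading.

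Four further points bear on the limits of the concern:

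- **The BPRS still has a use at the end of a period.** A positive item after period 1 can prevent period 2, and referral is useful whenever ideation is found. This stands. However, in sequence AB the active period is already over by then, and in BA the active-period BPRS comes at the end of the trial.
- **The safety text is a summary.** It is given in brief and points to a Data and Safety Monitoring Plan that is not among the documents, so the call script may already contain the item. Section IX item viii also describes the contacts as using an adverse event checklist, without the word common. Reading that word as the Section VII frequency class is reasonable but is an inference.
- **Home testing.** A reader might infer from "Subjects will then mail back the devices and questionnaires so data can be downloaded" that a positive BPRS would sit unread in the mail. No passage says that the BPRS is a mailed form. The home procedure includes a live video call the next morning, when the full side-effect list is used. What remains is that neither the arrival and morning lists in Measurements and Equipment—Clinical nor the home procedure names the BPRS.
- **Tolerability evidence.** A reader might also infer that psychiatric tolerability would rest on last-night readings in completers alone. Adverse events are monitored throughout and for 2 weeks after the last dose, so this does not follow.

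**Conclusion.** The point holds as a gap in structured detection, not as a failure of the stopping rule. As described in this document, the BPRS suicidality item is first asked on treatment after about 97% of the nominal doses, and no structured suicidality question is described in between. Under uniform onset over 30 days, asking it at contacts already scheduled would shorten the mean time to a structured question from 15.0 to about 2.9 days.

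This rests on three assumptions: that onset is uniform, that common in the call description follows the Section VII classes, and that the unseen Data and Safety Monitoring Plan does not already put the item on the calls. If that plan does so, the remaining issue is alignment of the text. The change is worth making because it is cheap and concerns a serious risk, although other routes of detection exist.

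**What to change.** 1. Add the BPRS suicidality item, and the events in the stopping criteria by name, to the script for the calls already scheduled (days 1, 3, 7, 14, 21 and 28, and the two calls after completion). If the Data and Safety Monitoring Plan already provides for this, align the Safety Monitoring text in Section V with it.
2. State in Measurements and Equipment—Clinical that the BPRS is part of the visit, and when in the visit it is done. State in the home-testing procedure that it is done on the existing live video call.
3. Have the sponsor reconcile three passages: the BPRS schedule and the immediate-assessment and discontinuation text in Section V, and the stopping criteria in Section VII. The Section V text ends participation when suicidality is judged related; the Section VII list stops a treatment period and does not mention relatedness. What should follow a positive answer is for the sponsor to settle; no clinical rule is proposed here.

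The cost is a revised call script and case report form, slightly longer calls, and more low-grade positive answers for the study physician to review. No visit is added.
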